11.2.1. Missing Data

Missing dates and times in the AE data will be handled as described in [Section 11.11.1](#). Concentrations that are below limit of quantification (BLQ) in the PK data will be handled as described in [Section 11.9.2](#).

There will be no imputations of other missing data. All subjects will be included into the safety analyses as far as the data permit.

11.3. Study populations

11.3.1. Safety analysis set

The safety analysis set will include all subjects who received at least 1 dose of IMP (anifrolumab or placebo) and for whom any safety post-dose data are available.

Unless otherwise stated the safety analysis set will be used for the presentation of all demographic and disposition data, as well as all safety, tolerability and immunogenicity analyses. Exposure to IMP will also be presented using the safety analysis set.

11.3.2. Pharmacokinetic analysis set

The PK analysis set will consist of all subjects in the safety analysis set for whom at least 1 of the primary PK parameters can be calculated, and who have no major protocol deviations thought to impact on the analysis of the PK data.

The exclusion of any subjects or time points from the calculation of the PK parameters will be documented by the PK Scientist including the reason(s) for exclusion.

The available concentration data and PK parameter data for any subjects excluded from the PK analysis set will be listed only. Concentration data for subjects excluded from the PK analysis set will be presented in the individual subject figures of concentration versus time plots.

11.4. Determination of Sample Size

The sample size is not based on statistical considerations. With a sample size of 6 subjects treated with active treatment there is 80% probability to observe at least one event of an AE that occurs with an incidence of 24% in the studied population.

11.5. Protocol Deviations

Protocol deviations are considered any deviation from the clinical study protocol relating to a subject, and include the following:

- Inclusion/exclusion criteria deviations
- Dosing deviations (e.g., incorrect treatment received, injection was not administered correctly)
- Time window deviations for safety and/or PK assessments, if applicable
- Subjects receiving prohibited concomitant medications
- Other procedural and study conduct deviations recorded by the clinical unit on a protocol deviation log

The criteria for the assessment and reporting of protocol deviations will be stipulated in a separate study-specific protocol deviation specification (PDS) document. This will include a Windows Allowance Document (WAD) which stipulates tolerance windows for safety and PK assessments. Measurements performed within these tolerance windows will not be considered as protocol deviations and will not be reported.

All protocol deviations will be discussed at the data review meeting prior to database hard lock in order to define the analysis sets for the study.

Important protocol deviations will be listed by subject.

Protocol deviations will be handled in accordance with PAREXEL SOPs.

For handling of protocol amendments, see [Section 3.6](#).

11.6. Subject Disposition

A randomization listing will be presented and include the following: each subject's randomization number, the subject's full enrolment number, the treatment to which the subject has been randomized and the country where the study center is located.

Subjects and/or data excluded from the PK analysis set will be listed including the reason for exclusion. Subject disposition will be summarized by treatment (dose of anifrolumab/ROA

or pooled placebo) and will include the following information: number of subjects randomized and dosed, number and percentage of subjects completing the study and the number and percentage of subjects who were withdrawn (including reasons for withdrawal). Disposition data will be presented based on all subjects randomized.

Subject discontinuations will be listed including the date of study exit, duration of treatment (time [in days] since dosing) and reason for discontinuation. A listing of informed consent response will also be presented.

11.7. Demographic and Baseline Data

Demographic variables (age, gender, race, ethnicity, height, weight and BMI) will be listed by subject. Demographic characteristics (age, gender, race and ethnicity) and subject characteristics (height, weight and BMI) will be summarized separately, by treatment and overall, for all subjects in the safety analysis set. The denominator for percentages will be the number of subjects in the safety analysis set for each treatment or for all subjects as applicable.

Medical history data will be listed by subject including visit, description of the disease/procedure, Medical Dictionary for Regulatory Activities (MedDRA) System Organ Class (SOC), MedDRA Preferred Term, start date and stop date (or ongoing if applicable).

11.8. Prior and Concomitant Medication and Drug Administration

11.8.1. Prior and concomitant medication

Prior medications are those that started and stopped prior to dosing with IMP; all medications taken after IMP dosing are considered as concomitant (including medications that started prior to dosing and continued after).

Prior and concomitant medication will be listed by subject and will include the following information: reported name, Preferred Term, the ROA, dose, frequency, start date/time, flag for whether the medication is prior or concomitant, duration and indication. Prior and concomitant medication will be coded according to the sponsor's drug dictionary.

The duration will be calculated as:

$$\text{Duration} = \text{end date/time} - \text{start date/time}$$

The duration may be presented in hours or days in the listing depending on the applicability to the emerging data. For medications with partial or completely missing start date/times and/or end date/times, the duration will not be calculated.

Medications with missing or partial start date/time and/or end date/time such that it is not possible to classify as prior or concomitant will be considered as concomitant in the listings.

11.8.2. Drug administration

Drug administration dates and times will be listed for each subject, including the location of the injection site for SC dosing and including the infusion volume, start and stop time for IV dosing. Any interruptions in the IV infusion will also be included in the listing.

11.9. Pharmacokinetic analysis

11.9.1. Pharmacokinetic parameters

Where possible, the following PK parameters will be assessed for anifrolumab on plasma concentrations.

Primary PK parameters

AUC	Area under serum concentration-time curve from time zero extrapolated to infinity
AUC _(0-t)	Area under the serum concentration-time curve from time zero to time of last quantifiable concentration
C _{max}	Observed maximum serum concentration

Secondary PK parameters

t _{max}	Time to reach maximum plasma concentration
λ _z	Terminal elimination rate constant
CL	Total body clearance after intravenous administration
CL/F*	Apparent total body clearance after extravascular administration estimated as dose divided by AUC
V _z	Apparent volume of distribution during the terminal phase after intravenous administration
V _z /F*	Apparent volume of distribution during the terminal phase after extravascular administration

* After SC administration only

The following diagnostic parameters for serum PK analysis will be listed, but not summarized:

λ_z upper and lower	The time interval (h) of the log-linear regression to determine $t_{1/2}$
λ_z, N	Number of data points included in the log-linear regression analysis
Rsq_adj	Regression coefficient adjusted for λ_z, N , Goodness of fit statistic for calculation of λ_z
%AUC _{extr}	Percentage of AUC obtained by extrapolating the area under the serum concentration-time curve to infinity from the time of the last quantifiable concentration using λ_z

Additional PK parameters may be determined where appropriate.

11.9.2. Derivation of pharmacokinetic parameters

The calculation of the PK parameters will be performed by Quantitative Clinical Development, PAREXEL. PK parameters will be derived using non-compartmental methods with , or higher and/or , or higher. All descriptive and inferential statistical computations will be performed using , or higher.

PK analysis will, where possible, be carried out using actual times recorded in the raw data. If actual times are missing, nominal times will be used.

For Cohort 3 subjects, actual administered dose after correction for amount left over in the dosing equipment may be used for PK analyses.

Serum concentrations which are BLQ prior to the first quantifiable concentration will be set to a value of zero. After the first quantifiable concentration, any BLQ serum concentrations will be set to missing for all concentration profiles. Where 2 or more consecutive concentrations are BLQ at the end of a profile, the profile will be deemed to have terminated and therefore any further quantifiable concentrations will be set to missing for the calculation of the PK parameters.

If an entire concentration-time profile is BLQ, the profile will be excluded from the PK analysis.

Terminal elimination half-life is estimated as $(\ln 2)/\lambda_z$, where λ_z refers to the terminal elimination rate constant, estimated by log-linear least squares regression of the terminal part of the concentration-time curve. For the determination of λ_z , the start of the terminal elimination phase for each subject will be defined by visual inspection and will be the first point at which there is no systematic deviation from the log linear decline in plasma

concentrations. A minimum of 3 data points will be used in calculating λ_z , and the duration of time over which PK blood samples were collected will be at least twice the subsequently estimated terminal half-life. Where an elimination half-life is estimated to be more than half of the PK collection interval, it will be flagged, commented upon in the study report and interpreted with caution. AUC is estimated by $AUC_{(0-t)} + C_{\text{last}}/\lambda_z$ where C_{last} is the observed last quantifiable drug concentration. The AUC values where the percentage extrapolation is greater than 20% will be listed but excluded from summary statistics.

AUCs (including AUC and $AUC_{(0-t)}$) will be calculated using the linear trapezoidal method when concentrations are increasing and the logarithmic trapezoidal method when concentrations are decreasing.

The minimum requirement for the calculation of AUC will be the inclusion of at least 3 consecutive serum concentrations above the lower limit of quantification (LLOQ), with at least 1 of these concentrations following C_{max} .

11.9.3. Presentation of pharmacokinetic data

A listing of PK blood sample collection times, as well as derived sampling time deviations (where applicable) will be provided. Serum concentrations and PK parameters of anifrolumab will be summarized by treatment (dose level of anifrolumab and ROA) using appropriate descriptive statistics. Where possible, the following descriptive statistics will be presented: n, geometric mean, geometric CV, arithmetic mean, arithmetic SD, arithmetic CV, median, minimum and maximum. For t_{max} , only n, median, minimum and maximum will be presented.

The geometric mean is calculated as the exponential of the arithmetic mean calculated using log-transformed data.

The CV% is calculated as $100 \cdot \sqrt{(\exp(s^2) - 1)}$ where s is the SD of the log-transformed data.

The following rules will apply to presentation of PK data:

- For PK concentration data, the listings will be presented to the same number of significant figures as the data received from the bioanalytical laboratory; for PK parameters, the listings will be presented according to the following rules:
 - C_{max} – will be presented to the same number of significant figures as received from the bioanalytical laboratory
 - t_{max} , λ_z lower and upper time limit – will be presented as received in the data, usually to two decimal places

-
- AUC, AUC_(0-t), CL/F, CL, V_z, V_z/F, R squared adjusted will be presented to three significant figures
 - λ_z – will be presented to four significant figures
 - λ_z , N will be presented as an integer (no decimals)
 - %AUC extrapolated will be presented to two decimal places
- For PK concentration data all descriptive statistics will be presented to four significant figures with the exception of the minimum and maximum which will be presented to three significant figures
 - For PK parameter data the descriptive statistics will be presented according to the following rules:
 - C_{max}, AUC, AUC_(0-t), CL/F, CL, V_z, V_z/F – all descriptive statistics will be presented to four significant figures with the exception of the minimum and maximum which will be presented to three significant figures
 - λ_z – all descriptive statistics will be presented to five significant figures with the exception of the minimum and maximum which will be presented to three significant figures
 - t_{max} – all descriptive statistics will be presented as received in the data, usually to two decimal places

Serum concentrations that are BLQ or if there are missing values (e.g., no result [NR]) will be handled as follows:

- Where there is NR, these will be set to missing.
- At a time point where less than or equal to 50% of the values are BLQ, all BLQ values will be set to the LLOQ, and all descriptive statistics will be calculated.
- At a time point where more than half of the values are BLQ, the mean, SD, geometric mean and CV% will be set to Not Determined (ND). The maximum value will be reported from the individual data, and the minimum and median will be set to BLQ.
- If all values are BLQ at a time point, no descriptive statistics will be calculated for that time point. Not applicable (NA) will be written in the field for standard deviation and CV% and BLQ will be written in fields for mean, geometric mean, minimum, median and maximum.
- The number of BLQ values (n below LLOQ) will be reported for each time point.

Data from subjects excluded from the PK analysis set will be included in the data listings, but not in the descriptive statistics.

Individual serum concentrations versus actual time will be plotted in linear and semi logarithmic scale with separate plots for each subject.

Combined individual serum concentration versus actual times will be plotted in linear and semi logarithmic scale. Plots will be grouped by dose level of anifrolumab and ROA.

Arithmetic mean serum concentration (\pm SD) versus nominal sampling time will be plotted in linear and semi logarithmic (no SD presented) scale with each dose level of anifrolumab and ROA overlaid on the same figure.

For mean plots, BLQ values will be handled as described for the summary tabulations; for individual plots serum concentrations which are BLQ prior to the first quantifiable concentration will be set to a value of zero (linear plots only). After the first quantifiable concentration, any BLQ serum concentrations will be regarded as missing. All combined individual and mean plots will be based on the PK analysis set. Individual subject plots will be based on the safety analysis set (excluding any subjects receiving placebo).

Finally, scatter plots showing the individual PK parameters and geometric mean versus dose level/ROA will be presented for C_{\max} and AUC.

11.9.4. Statistical analysis of pharmacokinetic data

No inferential statistical analysis of the PK data will be performed. All PK data will be summarized using descriptive statistics only.

11.10. Analysis of Immunogenicity Data

The results of the ADA assessments will be listed for each subject and time point. This will include the confirmatory assay (positive/negative) and the measured titers where appropriate. Summary tables will be presented, by treatment (dose of anifrolumab/ROA or pooled placebo), for the number and percentage of subjects with positive/negative results at each time point, based on the safety analysis set.

In addition, the ADA titers (n, median, minimum and maximum) will be summarized by treatment (dose of anifrolumab/ROA or pooled placebo) for all subjects with a positive confirmatory assay at each time point; this tabulation will include a summary of the highest titer across all time points for each subject.

11.11. Analysis of Safety Data

Safety data (scheduled and unscheduled) will be presented in the data listings. Continuous variables will be summarized by treatment (dose level of anifrolumab/ROA or pooled placebo, unless otherwise stated) using descriptive statistics (n, mean, SD, minimum, median, maximum). Categorical variables will be summarized in frequency tables (frequency and percentage) by treatment (dose level of anifrolumab/ROA or pooled placebo, unless otherwise stated). The analysis of the safety variables will be based on the safety analysis set.

11.11.1. Adverse events

All AEs will be coded using MedDRA vocabulary, and will be listed for each subject. A treatment-emergent AE (TEAE) is defined as an AE with onset (start date/time) after dosing on Day 1.

Adverse events with missing start dates/times will be handled as follows for classification as treatment-emergent:

- If the start date is completely missing but the end date is known and shows that the AE ended on or after the date of dosing, then the start date will be imputed as the date of dosing; if the end date is known and shows that the AE ended before the date of dosing, then the screening date will be used for the start date. If the end date is non-informative (i.e., is missing or does not contain enough information), the start date will be imputed as the date of dosing;
- If only the start day is missing the day will be imputed as the date of dosing if the known month is the same month as dosing occurred. If the end date is known and shows that the AE ended before dosing occurred the date will be imputed as 01. If the end date is non-informative (i.e., is missing or does not contain enough information), the start date will be imputed as the date of dosing in the known month. If the month is not the same as the month of dosing the date will be imputed as 01;
- If the start day and month are missing the date will be imputed as the date of dosing in the known year unless the end date is known and shows that the AE ended before dosing; in which case the start day and month will be imputed as 01Jan or with the date of screening if this is later. If the end date is non-informative (i.e., is missing or does not contain enough information), the start date will be imputed as the date of dosing in the known year. If the year is not the year of dosing then the date will be imputed as 01Jan or with the date of screening if this is later.
- Missing times will be imputed as 00:00 h or with the time of dosing for events starting on the dosing day.

Adverse events will be summarized by treatment, SOC and Preferred Term, including tabulations by causality and severity (mild, moderate and severe). A separate tabulation will be presented for AEs of special interest. Listings of SAEs, AEs that led to discontinuation (DAEs) and AEs that led to death will also be presented.

The following information will be included in the listings: verbatim term, SOC, PT and lowest level term, start date/time, end date/time, time from dosing, causality, action taken, whether the AE was classified as serious and the outcome.

All tabulations will include the number and percentage of subjects and will be presented by dose level of anifrolumab/ROA or placebo. Placebo subjects will be presented separately for each corresponding dose level/ROA and pooled for all the tabulations. In addition a separate tabulation will be presented showing the number of events by treatment and PT.

Finally an overview of all AEs will be presented, separately for the number and percentage of subjects and the number of events. This will include categories for any AE, AEs with outcome of death and SAEs.

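### Section 11.11.1: adverse events imputed to the time of dosing fail the treatment-emergent definition that the imputation is meant to serve

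*Protocol*

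**What the plan says.** All the relevant text is in Protocol Section 11.11.1.

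- Definition: "A treatment-emergent AE (TEAE) is defined as an AE with onset (start date/time) after dosing on Day 1".
- Purpose of the imputation rules: "Adverse events with missing start dates/times will be handled as follows for classification as treatment-emergent".
- Start date wholly missing, end date informative: if the end date shows that "the AE ended on or after the date of dosing, then the start date will be imputed as the date of dosing". A non-informative end date leads to the same result.
- Day missing: "If only the start day is missing the day will be imputed as the date of dosing", provided the known month is the month of dosing.
- Day and month missing: "If the start day and month are missing the date will be imputed as the date of dosing in the known year".
- Times: "Missing times will be imputed as 00:00 h or with the time of dosing for events starting on the dosing day".
- Events shown to have ended before dosing go to an earlier date instead (the screening date, the first of the month or 1 January, depending on the pattern).
- Tables: "Adverse events will be summarized by treatment, SOC and Preferred Term". Of the overview the section says: "This will include categories for any AE, AEs with outcome of death and SAEs". Neither sentence mentions the treatment-emergent flag.

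Section 11.1 says that no separate SAP will be written and allows an abbreviated one only for changes. This section is therefore the working specification.

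**The concern.** The date rules separate two kinds of AE with an incomplete onset: those shown to have ended before dosing, and those that might have started after it. The second kind goes to the dosing date, which is the usual cautious choice. But the definition requires onset strictly after dosing, and the time rule places the onset exactly at dosing. Both kinds then have the same status, not treatment-emergent, and the imputation achieves nothing for the events it was written for.

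The pattern most likely to matter needs no date imputation at all: an AE known to have started on Day 1 whose clock time was not recorded. Day 1 is when acute reactions to the dose would be expected.

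Safety and tolerability are a primary objective (Section 6.1), so the rule that assigns events to treatment should give the result it was written to give.

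**Working it through.** **The plan's own figure.** The protocol gives no figure on this point. Its one probability statement (Section 11.4: six active subjects, 24% incidence, 80% chance of at least one event) reproduces as 1 − 0.76^6 = 0.807. The point does not depend on it.

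**Classification check.** Inputs are the definition, the date rules and the time rule of Section 11.11.1. Let d be the date and time of dosing and s the imputed onset. As written, an AE is treatment-emergent if s > d. The alternative tested is s ≥ d. The results do not depend on the value of d. Unless the table says otherwise, the clock time is missing.

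| What is known about onset | Imputed s | s > d | s ≥ d |
|---|---|---|---|
| Nothing; ended on or after the dosing date | d | no | yes |
| Nothing; end date non-informative | d | no | yes |
| Dosing month, day missing, not shown to have ended before dosing | d | no | yes |
| Dosing year, day and month missing, not shown to have ended before dosing | d | no | yes |
| Day 1, time missing | d | no | yes |
| Nothing; ended before dosing | screening date | no | no |
| Earlier month, day missing | first of that month | no | no |
| Later month, day missing | first of that month | yes | yes |
| Later year, day and month missing | 1 January | yes | yes |
| Day 2, time missing | 00:00 on Day 2 | yes | yes |
| Date imputed to Day 1, recorded post-dose clock time | Day 1 at that time | yes | yes |

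In the first five rows s − d = 0. As written, 0 of 5 are treatment-emergent; with equality allowed, 5 of 5 are. The other six rows are the same under both rules. Reading the time rule as 00:00 on Day 1 would not help, because that onset precedes a dose given later that day.

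**Effect on the tables.** There are two cases, and only one can apply.

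1. *The tables use the flag.* Events in the first five rows drop out. If such an event is a subject's only one in a table row, an active arm's incidence in that row falls by 1/6 = 16.7 percentage points. If the subject has another qualifying event in the row, the change is zero.
2. *The tables cover all AEs, as the wording says.* The boundary changes no incidence. Pre-dose events are then counted under a treatment not yet received. Section 12.2.1 collects SAEs from consent and other AEs from randomization, Section 12.3 collects AESIs from consent, and Section 8.9.1 puts randomization on the morning of dosing. The exposure is therefore SAEs and AESIs from consent, plus other AEs in the interval between randomization and dosing.

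**The case against.** The strongest reply is that the intent is plain. The rules are introduced as serving treatment-emergent classification, and only an at-or-after reading gives them a purpose, so a sensible programmer would code it that way. Affected events should also be few. Start and stop date and time are collected for every AE (Section 12.2.3), subjects are resident from Day −1 to Day 3 (Section 7.1), and missing data are queried until resolved (Sections 10.4.1 and 10.5). No rule in the protocol acts on the flag: Cohort 3 opens on the PI's judgement (Section 8.6), and the example for stopping the study uses related SAEs (Section 7.5.4). All AEs are listed with time from dosing, so none is hidden. The rule is the same for active and placebo.

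All of this stands, and it limits the consequence. It does not remove the inconsistency: no sentence says that onset equal to dosing counts, and a prespecified rule should not rely on a programmer to override it.

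A reader might infer more than the text supports:

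- *That the boundary and the pre-dose counting both bias the incidences.* They are alternatives, depending on whether the tables use the flag.
- *That every AE with an imputed date is lost.* One with a recorded post-dose clock time, or imputed to a later month or year, still qualifies.
- *That all AEs from Day −1 enter the tables.* Table 1 does ask about AEs on Day −1, but Section 12.2.1 starts collection of non-serious AEs at randomization. That mismatch is a separate matter.
- *That reactions during an infusion are excluded.* Section 11.11.1 does not say end of dosing. The reading is possible because Cohort 2 is infused over 30 minutes and Cohort 3 by pump, but it is an ambiguity and not a stated exclusion.

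**Conclusion.** The inconsistency is real. By the literal rule, an AE whose onset is imputed to the date and time of dosing is not treatment-emergent, contrary to the stated purpose of the imputation: five patterns affected, none classified as intended. The number of events in those patterns cannot be derived from the protocol and is probably small in a resident unit with 30 subjects. The 16.7-point shift is a conditional maximum for one subject in an active arm of six. It assumes that the tables use the flag and that the event is the subject's only one in the row. If the tables do not use the flag, the remaining defect is that a narrow set of pre-dose events is tabulated under treatment. The documents show no direction of bias between active and placebo. This is a minor correction to an analysis rule, not a must-fix.

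**What to change.** In Section 11.11.1:

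1. Define a TEAE as an AE with onset at or after the start of IMP administration (start of the IV infusion, first SC injection, or start of the SC pump infusion). This also settles the status of events that begin during administration.
2. State that an onset imputed to the date and time of dosing counts as treatment-emergent.
3. State that the AE summary tables and the overview are of TEAEs, and that pre-dose AEs are listed only.

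The change should be made before database lock and unblinding. It takes a few sentences, needs no new data and changes no procedure. TEAE counts may be slightly higher, because a Day 1 event with no recorded time will count even if it began shortly before the dose. That is the cautious direction the imputation already aims for.
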